7.2.2 Clinical Investigation Flow Chart

Procedures and outcome measures will be collected as described in the clinical investigation flow chart shown in Table 1.

Table 1 Clinical Investigation Flow Chart

Protocol requirements	Study Visit (D=Day)								
	Admission/ D0	D1	D2	D3	D4	D5	D6	D7	Study Termination ^e
Informed Consent	X								
Inclusion/ Exclusion criteria	X								
Randomization	X								
Complete physical exam	X								
Enter Device #	X								
Intake ^a	X								
Study Measurements ^b	X	X	X	X	X	X	X	X	X
Pro-Calcitonin, C-reactive protein, ferritin, D-dimer, CBC w/dif	X (+ serum/urine hCG for women who may be pregnant)	X		X		X		X	X
Comprehensive metabolic panel	X			X		X		X	X
Study labs drawn before 10am (Frozen blood sample, Immunokine panel (Luminex) including (TNF- α , IL-1 β , IL-6), Leukocyte flow cytometry		X	X	X		X		X	

Clinical Investigation Plan

	Study Visit (D=Day)									
Protocol requirements	Admission/ D0	D1	D2	D3	D4	D5	D6	D7	Study Termination ^e	
Device training ^c	X									
nVNS Stimulation Supervised ^c	X	X								
VNS Stimulation ^c		3X +prn	X							
Clinical Improvement Scale	X	X	X	X	X	X	X	X	X	
Daily Tx Log completed ^d	X	X	X	X	X	X	X	X	X	
Concomitant medications	X	X	X	X	X	X	X	X	X	
Adverse Event	X	X	X	X	X	X	X	X	X	

- ^a Includes collection of basic demographics (DOB, Race, Sex, Smoking Status, County/Region), medications, comorbidities CoViD-19 test results)
- ^b Includes height/weight (BMI), temperature, blood pressure, O₂ saturation, PaO₂/FiO₂ ratio, shortness of breath assessment, cough assessment
- ^c For the active study arm. Includes record of treatment (time and number of doses administered)
- ^d The following parameters will be recorded daily: Oxygen dependence & data, ventilator dependence & data, discharge data, survival, device treatment record (active study arm only)
- ^e Study completion will be determined by discharge, transition to mechanical ventilation and/or if the patient is unable to continue

7.3 Discussion and Justification of Clinical Investigation Design, Including the Choice of Control Groups

The study design (randomized, including a control group) was chosen to evaluate the usefulness of the gammaCore® Sapphire device for symptom improvement in patients suffering CoViD-19 related respiratory distress compared to standardized institution treatment only.

During hospitalization, the study patients, if able, will administer gammaCore® as prescribed for all acute respiratory attacks or shortness of breath, and also prophylactically. If patients are unable, study personnel may assist.

7.3.1 Prior and Concomitant Medication and Procedures

Medication, which is considered necessary for the patient's safety and well-being, may be given at the discretion of the Investigator.

The study team will document all concomitant medication usage during the investigation in the CRF.

7.4 Selection of Population for the Clinical Investigation

7.4.1 Number of Patients

After the first 20 patients have been enrolled and completed the study at Allegheny General Hospital, the investigator will conduct an interim analysis and submit findings to the IRB for approval to increase the enrollment up to 60 patients (30 patients per arm). Up to 90 patients are expected to be screened.

7.4.2 Inclusion Criteria

The patients have to meet all of the following criteria to be eligible to enter the investigation:

1. Patients (age 18 years and older) who have tested positive or suspected/presumed positive for CoViD-19 using PCR real-time test
2. Patients with cough, shortness of breath or respiratory compromise (RR>24/min, increased work of breathing)
3. O₂ Saturation less than or equal to 96% on room air or sensation
4. Agrees to use the gammaCore Sapphire device as per protocol and to follow all of the requirements of the study including recording required study data
5. Permission for early am blood draw to freeze for subsequent lab tests and sequencing as related to CoViD-19 sequelae
6. Patient is able to provide signed and witnessed Informed Consent

7.4.3 Exclusion Criteria

Patients meeting any of the following criteria cannot be included in this research study:

1. On home/therapy oxygen (i.e. for COPD patients) at baseline prior to development of CoViD-19
2. Already using gammaCore® for other medical conditions
3. A history of aneurysm, intracranial hemorrhage, brain tumors, or significant head trauma
4. Known or suspected severe atherosclerotic cardiovascular disease, severe carotid artery disease (e.g., bruits or history of transient ischemic attack or cerebrovascular accident), congestive heart failure, known severe coronary artery disease, myocardial infarction documented within past 90 days, or current or recent history of life-threatening arrhythmia (sustained ventricular tachycardia, ventricular fibrillation, second or third-degree heart block, uncontrolled atrial fibrillation or uncontrolled atrial flutter)
5. Patients with clinically significant hypertension, hypotension, bradycardia, or tachycardia (as per investigator discretion)

6. Current implantation of an electrical and/or neurostimulator device, including but not limited to a cardiac pacemaker or defibrillator, vagal neurostimulator, deep brain stimulator, spinal stimulator, bone growth stimulator, or cochlear implant
7. Current implantation of metal cervical spine hardware or a metallic implant near the gammaCore® stimulation site
8. Belongs to a vulnerable population or has any condition such that his or her ability to provide informed consent, comply with the follow-up requirements, or provide self-assessments is compromised (e.g. homeless, developmentally disabled and prisoners)
9. Compromised access to peripheral vein for blood
10. Pregnant women
11. Patients with active cancer or those who have had recent cancer treatment

Before enrollment into the study, patients must meet all of the following inclusion criteria and none of the following exclusion criteria.

7.4.4 Removal of Patients from the Clinical Investigation

Patients are free to discontinue participation in the investigation at any time, without prejudice to further treatment. Patients who discontinue the investigation should always be asked about the reason(s) for their discontinuation and about the presence of any adverse event (AE)/adverse device effect (ADE) and, if possible, be assessed by a Clinical Investigator.

Patients may be withdrawn from investigation treatment and assessments at any time, if deemed necessary by the Clinical Investigator.

Specific reasons for withdrawal of patients from this investigation are:

- The decision of a patient to withdraw from the investigation (including if the patient withdraws informed consent)
- Unacceptable adverse event
- Patient lost to follow-up; or
- Patient is non-compliant with study procedure

In case of withdrawal, AEs/ADEs should be followed up.

Incorrectly enrolled patients will be withdrawn from further investigation and assessments. A protocol deviation will be submitted to the IRB via a prompt report form.

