7.10.1.1 Data Sets to be Analysed

The intention to treat (ITT) population includes all randomized subjects with at least 1 verified treatment post-training during study period. The ITT population will be analyzed using the subject's randomized treatment regardless of which treatment the subject actually received.

Subjects with major protocol deviations will be excluded from the per-protocol (PP) analysis set. Subjects not taking the study treatment in the prescribed manner more than 33% of the time will be excluded from the PP analysis set. Additional subjects with exclusionary protocol deviations will be identified prior to database finalization and unblinding. Analyses for the PP will be conducted according to the randomized treatment.

All subjects entering the study will be included in the safety population. Analyses for safety population will be conducted according to the treatment actually received.

Definitions

Generally, a baseline measurement refers to the last non-missing assessment made before the first administration of study treatment (at e.g. screening and baseline).

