7.10.2 Handling of Drop-outs and Missing Data

Outliers will be included in summary tables and listings, and will not be handled separately. Available data from prematurely withdrawn patients will be included in the analysis as far as possible. If data are only partially completed, the available data will be reported as an per protocol evaluation

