7.12 Deviations from the Clinical Investigation Plan

Every effort should be made to comply with the requirements of the protocol. If the changes or deviations may affect the rights, safety, or welfare of participants, IRB/IEC approval is required. Deviations will be recorded with an explanation for the change. Corrective action will be implemented to avoid repeat deviations.

The reasons for any patient's withdrawal and discontinuation from the investigation will be recorded. If such discontinuation is because of problems of safety or lack of effectiveness, the patient will still be followed up in the investigation, if possible.

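### Outcome collection is not secured after withdrawal for reasons other than safety or lack of effectiveness, and the resulting loss may be more likely in the device arm

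*Combined protocol and SAP*

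**What the plan says.** Section 7.4.4 (Removal of Patients) states: "Patients may be withdrawn from investigation treatment and assessments at any time, if deemed necessary by the Clinical Investigator". One of its listed reasons is "Patient is non-compliant with study procedure", with no threshold and no restriction to one arm. Incorrectly enrolled patients are, without discretion, taken out of further assessments. The only follow-up the section requires is for safety: "In case of withdrawal, AEs/ADEs should be followed up".

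Section 7.12 (Deviations) adds: "If such discontinuation is because of problems of safety or lack of effectiveness, the patient will still be followed up in the investigation, if possible". No equivalent sentence covers other reasons.

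Section 7.10.2 says: "Available data from prematurely withdrawn patients will be included in the analysis as far as possible". Section 7.8.5 requires deaths within 30 days of study treatment to be reported to the IRB.

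Section 7.10.1.1 has the intention-to-treat set "analyzed using the subject's randomized treatment regardless of which treatment the subject actually received". The same section deals with poor compliance by exclusion from the per-protocol set, when treatment is not taken as prescribed more than 33% of the time.

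The protocol note in section 7.2.1.1 also ends study participation when a patient can no longer continue treatments. Section 7.2.1.5 ends it when the patient is unable to continue.

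**The concern.** An analysis by randomised arm needs outcomes from patients who stop complying as well as from those who continue. Section 7.4.4 does not distinguish stopping the device from leaving the study, so a patient who stops using it can also stop contributing data on oxygen support, ventilation, discharge and survival. These are the clinical events the objectives set out to compare.

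The two arms are not equally exposed to this. The device arm has three scheduled treatments a day, as-needed use, and a treatment log. It also has an exit worded in terms of treatments that the control arm does not receive. If leaving is related to prognosis, the patients still observed in the device arm are no longer comparable with the controls.

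**Working it through.** **Is any reason for withdrawal left without outcome follow-up?** The provisions that might cover it are:

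- *Adverse event follow-up (7.4.4, 7.8.4.2).* This applies after any withdrawal, but 7.8.4.2 describes it for events ongoing at that point. It does not provide for oxygen support or discharge, or clearly for a later ventilation.
- *Death reporting (7.8.5).* This is a reporting duty to the IRB, counted from receipt of the study drug, device or intervention. Its application to control patients, who receive no device, is unclear.
- *Use of available data (7.10.2).* This keeps what has been collected. It promises no further collection.
- *Continued follow-up (7.12).* This covers safety and lack of effectiveness only, where possible.

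Non-compliance, incorrect enrolment and a patient's decision to stop for other reasons therefore carry no commitment to collect clinical outcomes.

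**How large could the effect be?** The plan gives no event rate, withdrawal rate or power calculation, so there is no figure to reproduce. The only input from the documents is 30 patients per arm (7.4.1). The rest are assumptions: true risk of ventilation *R* = 20% in both arms, no treatment effect, no loss in the control arm, and a share *w* of 10% or 20% of the device arm lost (3 or 6 of 30). Let *r* be the risk in those lost divided by the risk in those kept.

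If *p* is the risk in those kept, then *R* = (1 − *w*)*p* + *w r p*, so *p* = *R* / (1 − *w* + *w r*).

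| *w* | *r* | Observed device-arm risk | Difference from 20% |
|---|---|---|---|
| 10% or 20% | 1 | 0.20/1.00 = 20.0% | 0 |
| 10% | 2 | 0.20/1.10 = 18.2% | −1.8 points |
| 10% | 3 | 0.20/1.20 = 16.7% | −3.3 points |
| 20% | 2 | 0.20/1.20 = 16.7% | −3.3 points |
| 20% | 3 | 0.20/1.40 = 14.3% | −5.7 points |
| 10% | 0.5 | 0.20/0.95 = 21.1% | +1.1 points |
| 20% | 0.5 | 0.20/0.90 = 22.2% | +2.2 points |

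Negative values favour the device.

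Control-arm loss shrinks the difference. With *r* = 3, 20% lost in the device arm and 10% in the control arm, it is 14.3% − 16.7% = −2.4 points. With 20% lost in both arms at the same *r*, it is 0.

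One result needs no assumption about risk. Each patient with an unknown outcome widens the best-case to worst-case bounds on an arm's proportion by 1/30 = 3.3 points, so 3 lost gives 10 points and 6 lost gives 20.

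**The case against.** A reader might infer that outcomes are lost selectively from the device arm and that the device is thereby made to look better. The documents do not support that:

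- Withdrawal for non-compliance is discretionary. The per-protocol rule in 7.10.1.1 implies that some poor adherers stay in with data.
- The listed reason concerns study procedure in general. Blood draws and daily assessments apply to both arms.
- Staff may assist with or give the treatment (7.3, 7.6). Patients without relief from acute treatment may receive standard care and resume later (7.2.1.1). Stopping for lack of benefit falls within the group that 7.12 does follow, where possible.
- Recovering patients may also stop complying, which would bias against the device.
- No withdrawal rates by arm are given. Section 7.10.4 reports only minor deviations in the first 20 patients, without withdrawals by arm.

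Nor would it be right to infer that patients who stop for other reasons have no follow-up at all, since adverse events are followed after every withdrawal. Section 7.10.1.1 does not strictly contradict 7.4.4 either: it says in which arm patients are analysed, not how long they are observed.

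On consequence, 7.10.1.2 calls all comparisons nominal. At 20% risk and 30 per arm, the 95% interval for a difference is about ±1.96 × √(2 × 0.2 × 0.8/30) = ±20 points, against which 5.7 points is 0.057 × 30 = 1.7 patients.

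All of this stands as a limit on what can be claimed. It does not close the gap. Calling the comparisons nominal leaves any bias in the estimates, and a wide interval does not allow for it. The separate SAP promised in 7.10.1 could say how missing outcomes are handled, but it could not supply outcomes that were never collected.

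**Conclusion.** The point holds as a gap in data collection. Followed as written, 7.4.4 and 7.12 can remove randomised patients' clinical outcomes after a post-randomisation event, and the device-use requirements make that event plausibly more common in the device arm.

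Whether bias results, how much, and in which direction cannot be determined from the documents. On the stated assumptions, equal to three-fold risk in those lost gives a false difference of 0 to 5.7 points in favour of the device. The sign reverses if lower-risk patients leave, and the difference vanishes if loss and risk are alike in both arms. The plan should be amended because the gap is avoidable at small cost; the documents do not show that the comparison is already distorted.

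**What to change.** 1. In 7.4.4, distinguish stopping the device from leaving the study.
2. For every randomised patient, keep recording oxygen support, ventilation, discharge and survival from the hospital record unless the patient withdraws consent for data use. Name explicitly those withdrawn for non-compliance, those incorrectly enrolled, and those who exit as unable to continue (7.2.1.1, 7.2.1.5).
3. Extend the follow-up sentence in 7.12 to all reasons for discontinuation, so that it agrees with 7.4.4.
4. Leave poor compliance to the existing per-protocol exclusion in 7.10.1.1.

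This changes data collection only, not when treatment stops. With complete follow-up *w* = 0, and both the illustrative bias and the width of the bounds become 0.

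The cost is amendment wording, some extra record abstraction (7.2.1.1 already transfers hospital-record data to the case report forms), and a check that the consent form covers data collection after withdrawal. No sample size changes, since none was calculated.

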7.5 Identification and Description of the Clinical Investigational Medical Device

7.5.1 Identification of the Clinical Investigational Medical Device

gammaCore Sapphire (non-invasive vagus nerve stimulator) is a multi-use, handheld, rechargeable, portable device consisting of a rechargeable battery, signal-generating and amplifying electronics, and a control button for the patient to control the signal amplitude. The device provides visible (display) and audible (beep) feedback on the device and stimulation status. A pair of stainless-steel surfaces, which are the skin contact surfaces (“stimulation surfaces”), allows the delivery of a proprietary electrical signal. The patient will apply electroCore-approved gel to the stimulation surfaces to maintain an uninterrupted conductive path from the stimulation surfaces to the skin on the neck. Tubes of electroCore-approved gel will be provided with each unit. The stimulation surfaces will be capped when not in use. gammaCore® produces a low-voltage electric signal consisting of five 5000-Hz pulses that are repeated at a rate of 25 Hz. The waveform of the electric pulses is approximately a sine wave with a peak voltage limited to 24 Volts when placed on the skin and a maximum output current of 60mA.

The signal is transmitted through the skin of the neck to the vagus nerve. gammaCore® allows for the patient to appropriately position and adjust the stimulation intensity level as instructed by the research team. Each stimulation is designed to be applied for 2 minutes, after which the device automatically stops delivering the stimulation. Each device allows for multiple treatments.

gammaCore® can deliver up to thirty 120-second stimulations within a 24-hour period. Once the maximum daily number of treatments has been reached, the device will not deliver any more stimulations until the following 24-hour period. (The stimulation automatically stops 120 seconds after the device is powered on). The gammaCore® Sapphire device includes a charging station to hold and charge the device.

Figure 1. gammaCore® Sapphire

Figure 2. gammaCore® Sapphire with Charging Station

The patient will apply conductive gel (supplied with the device) to the stimulation surfaces and then hold the nVNS device on the skin over the vagus nerve on the neck (between the trachea and the sternocleidomastoid muscle, over the carotid pulse). Details of device placement and operation will be provided in the Instructions for Use (IFU).

The gammaCore Sapphire device produces a proprietary, low voltage electric signal that generates an electric field in the vicinity of the vagus nerve when the device is placed in the intended location.

7.5.2 Packaging and Labelling of the Clinical Investigational Medical Device

The commercial packages will be used in this Clinical Investigation, all device packaging will be marked “For Clinical Investigation Only”.

7.5.3 Installation and Use of the Clinical Investigational Medical Device

A qualified research personnel (i.e. device trained) will train the study patients before they can start self-administration of stimulations. The gammaCore® Sapphire device will be used following the treatment assigned in this protocol.

7.5.4 Compliance with Device Usage

Patient will record all use of the device in a study log, trained study staff can assist the patient, as necessary. Compliance will be assessed in the hospital setting by the research staff.

7.6 Risk and Benefits of the Investigational Device and Clinical Investigation

The gammaCore Sapphire is being trialled for the acute and prophylactic treatment of CoViD-19 induced respiratory distress. The anticipated benefits include:

- No mechanical respirator required
- Significant reduction of number of days in hospital

There are no significant risks identified with the participation in this study however study patients can rarely experience transient symptoms such as:

- Muscle twitching, discomfort, or pain during stimulations
- Tingling, pricking or a feeling of “pins and needles” on the skin where the device is applied (paraesthesia or dysaesthesia) lasting beyond the treatment period
- Skin irritation/inflammation
- Dizziness

Study subjects will be exposed to potential risks and complications associated with gammaCore. These are anticipated to resolve shortly after discontinuation of the stimulation procedure without medical intervention or clinical sequelae. Occurrence of several of these events can be mitigated by the user repositioning the device on the neck and/or decreasing the stimulation intensity. Training on the positioning of the device and controlling the stimulation intensity is conducted at the time the device is provided to the subjects. In addition, the device is provided with detailed Instruction for Use. These potential anticipated adverse events include, but are not limited to:

- Application site discomfort (4.85%)
- Application site irritation/redness (3.74%)
- Local pain, face/head/neck area (including toothache) (3.00%)
- Muscle twitching and/or contractions, face/head/neck area (including facial droop and/or lip pull) (3.47%)
- Headache/migraine (2.56%)
- Dizziness (2.00%)
- Tingling, pricking or a feeling of “pins and needles” on the skin where the device is applied (paresthesia/dysesthesia) (1.63%)

NOTE: When all available safety data was pooled from all studies, the following AEs occurred in >1% of patients, but less than < 5% (there were no reported side effects that occurred in >5% of study patients) All adverse events occurred in at least 1 in 100 (1%) patients and are therefore “common”.

Risks associated with blood draws

- Pain or discomfort from needle
- Bleeding
- Infection

Pregnancy:

It is unknown whether gammaCore can harm an unborn child if used during pregnancy. If you are pregnant, you will not be allowed to participate in this study.

The product will be used at the hospital.

Each device is for single patient use. No device sharing will be done. Every patient will have an individual device throughout the study. It will be stored in patient room throughout the duration of the study and at completion will be discarded by study staff, according to institutional policy and following all regulations for disposal of infectious waste and electrical equipment.

All patients must undergo training at the hospital before starting treatment with the device in order to learn and optimize where and how to stimulate. Written information will also be provided.

All research staff included in study will be trained in the use of device. Patients will administer their own treatment unless unable to do so safely. Treatment can be administered by trained research staff, if necessary and with patient permission.

Site will be instructed to contact electroCore immediately if the product malfunctions and does not work as expected or if the device have been damaged or is suspected to have been damaged in some way. If patients are using it without clinical supervision, patients will report any product malfunctions to the PI and/or research staff. Should any type of malfunction occur, the patient would discontinue use of the device and the research staff will assess for any adverse events. Any device deficiencies/malfunctions will be reported to the PI, the IRB via a prompt report form and the device manufacturer. The device will be quarantined by the research staff and a new device will be provided to the patient.

The benefits of this study are estimated to outweigh the risks as the patient's improvement is expected to be considerably greater than any expected side effects..

